3.3.2 Disclosure Procedures

Following the Part I Education session, participants/co-participants who are deemed eligible will be invited to take part in a 90-minute virtual Part II Disclosure session. Study team members will contact the participant or dyad via phone to introduce the study (see 'STIM+ Disclosure Oral Script'). Disclosure procedures are summarized in Table 3.

1. **Consent** – Interested participants will undergo a separate consent procedure for Disclosure, given the differing level of risk in this portion as compared to the Education portion. Consent will be completed virtually following the same procedures as detailed above in the Education Procedures section.
2. **PET Disclosure**: All parent studies utilize the expertise and methods of [name] (head of PET imaging at University of Michigan) for PET analysis; this will ensure consistency across methods and interpretive messaging regardless of the parent study. Each participant's PET imaging will be reviewed by [name], who will provide both region-specific and total standardized uptake value ratio (SUVr) calculations of amyloid and tau burden and determinations of whether these ratios surpass normatively-referenced thresholds to indicate amyloid or tau positivity. We will share only positive vs. negative status and simplified qualitative risk estimates (e.g. positivity = 'increased risk/likelihood of Alzheimer's etiology'), given the current lack of validated quantitative models of AD risk based on amyloid and tau. The study team have developed a flexible disclosure protocol that provides written and graphic representations of the participant's amyloid results (see 'STIM+ Disclosure Slides'). The protocol will be adapted using standardized instructions prior to the session, to personalize each protocol to the participant. Personalization will be based on demographic factors and geographic location of the patient's home (to ensure identified resources are close by and accessible), and PET results (to ensure that appropriate recommendations and resources are given). PET results will be provided as a qualitative interpretation (i.e., Elevated vs. Not Elevated) of the presence or absence of significant burden for either of the abnormal proteins. Disclosure will also involve discussion that elevation on either/both proteins may indicate underlying AD pathology that may explain their current cognitive/behavioral symptoms. Following this summary, the protocol includes general recommendations and next steps for healthy aging (e.g., taking care of physical and emotional health, staying cognitively and socially engaged) and a list of informational and support resources. As with the Education Module, the disclosure protocol will include multiple 'checks for understanding' after each section to ensure that information communicated is being comprehended accurately by the participant and co-participant.

2. **Informal Between-Session Follow-Up:** Participants and DPOAs/LARs will be provided with contact information for the social worker and clinical psychologists at the time of disclosure; we will also track any additional requests for information, support, or resources between assessment sessions and provide such information as appropriate.

Participants and co-participants will each be compensated with \$10 per follow-up session completed, paid via check after the session.

Figure 2. Overview of Study Methods & Outcome Measures

3.4 OUTCOMES

In addition to measuring **preliminary interest in PET disclosure after STIM activities (Aim 1, Primary Outcome 1)** and **Disclosure Decision-Making Capacity (overall and by component; Aim 2, Primary Outcome 2)**, we will collect the following outcome measures post-disclosure for participants who complete this step (Aim 3). These measures will be completed over the phone or via virtual visit to allow for maximum flexibility. Of note, we will also administer the GDS-15 and BAI at each time point for the purpose of safety monitoring (see DSMP); these are not considered primary outcomes. A summary of the outcome measure respondents and timeline is provided in Table 4.

Primary Outcome 3.1 - Comprehension & Recall: The Personal Information and Meaning of Information accuracy scores will be totaled for all participants and co-participants. Mean, median, and standard deviation will be calculated. Exploratory analyses will evaluate trends in whether specific types of feedback information (e.g., neuroimaging vs. amyloid/tau burden) were better understood than others, and whether group differences exist (i.e., participants vs. co-participants, by race, by cognitive status).

Primary Outcome 3.2 - Positive and Negative Affective Scale – Short Form (PANAS-SF¹⁸): This 20-item scale asks respondents to rate the extent to which they are experiencing positive (e.g., excited, inspired) and negative (e.g., distressed, ashamed) emotions on a Likert-style scale ranging from '1 = Very Slightly or Not at All' to '5=Extremely.' The two subscale scores range from 10-50, with higher scores indicating higher positive or negative emotions, respectively. The PANAS has demonstrated strong psychometric properties for assessing emotions in older adults¹⁹. This measure will be administered to both participants and co-participants.

Primary Outcome 3.3 - Impact of Neuroimaging in Alzheimer's Disease (INI-AD): This measure assesses both positive and distressing reactions to disclosure of PET amyloid and tau results. The measure is adapted from the original Impact of Genetic Testing in Alzheimer's Disease scale²⁰ (used to measure reactions to genetic susceptibility testing results for AD genes), the scale was adapted to PET biomarker disclosure. This scale has been previously developed and used as part of the REVEAL study, and has the strength of assessing both positive and negative reactions and being specific to Alzheimer's disease. This measure will be administered to both participants and co-participants.

Primary Outcome 3.4 - Stigma Scale for Chronic Illness (SSCI-8²¹): The SSCI-8 demonstrates strong reliability for the measurement of both internalized and enacted stigma perceived by individuals with chronic neurological conditions. Respondents complete 8 items about experiences of stigma, rated on a Likert-style scale from 1 = 'Never' to 5 = 'Always.' This measure will be administered to participants only.

Primary Outcome 3.5 - Self-Efficacy for Managing Chronic Disease Scale (SECD²²): The SECD is a 6-item scale that measures perceived ability to self-manage the physical, emotional, and cognitive symptoms associated with their chronic disease. Items are listed on a 10-point scale ranging from 1 = 'Not at all confident' to 10 = 'Totally confident'. Though not previously applied to Alzheimer's disease specifically, psychometric properties for the assessment of self-efficacy across chronic conditions were strong (reliability ranging from 0.88-0.95²³). This measure will be administered to participants only.

Primary Outcome 3.6 - Future Time Perspective Scale (FTP²⁴): This 10-item scale measures the extent to which respondents feel that they have potential for productive and functional years ahead of them. Statements regarding positive and negative future time perspective are rated on a 7-point Likert-style scale, ranging from 1= 'Very untrue' to 7='Very true.' This measure will be administered to both participants and study partners.

Primary Outcome 4.1 - Preparedness for Caregiving Scale (PCS^{29,30}): This 8-item measure assesses the degree to which care partners of persons with cognitive impairment (e.g., MCI, DAT) perceive they are prepared for and able to manage various domains of caregiving such as providing physical care and emotional support, setting up in-home support services, and coping with stress due to caregiving. Items use a 5-point likert scale ranging from 0 = 'Not at all prepared' to 4 'Very well prepared'. The PCS has demonstrated strong psychometric properties for assessing perceived readiness for caregiving among family members of persons with Alzheimer's disease dementia. This measure will be administered to study partners only.

Primary Outcome 4.2 - Revised Scale for Caregiving Self-Efficacy (RSSE³¹): The Revised Scale for Caregiving Self-Efficacy is a 15-item scale consisting of 3 sub-scales, each containing 5-items, designed to measure perceived ability to manage aspects related to caregiving among caregivers of persons with dementia. A single subscale consisting of 5-items will be used to measure co-participant's perceived ability to manage the emotional stresses associated with caregiving. This measure will be administered to study partners only.

Table 4. Outcome Measure Summary

Construct/Measure	Group (Participant, Study Partner, or Both)	Pre- Disclosure (Education Session)	Data Collection		Timepoint	
			Immediate Post- Disclosure	1-week	6-weeks	
Positive and Negative Affective Scale – Short Form	Both	X	X	X	X	
Impact of Neuroimaging in Alzheimer's Disease	Both		X	X	X	
Future Time Perspective Scale	Both	X	X	X	X	
Stigma Scale for Chronic Illness	Participant	X	X	X	X	
Self-Efficacy for Managing Chronic Disease Scale	Participant	X	X	X	X	
Revised Scale for Caregiving Self-Efficacy	Study Partner	X		X	X	

Preparedness for Caregiving	Study Partner	X		X	X
-----------------------------	---------------	---	--	---	---

SECTION 3.5 DATA MANAGEMENT & ANALYSIS

3.5.1 Data Management & Entry

Only IRB approved study personnel will have access to study documents/data. Signed consent paperwork and will be uploaded into the participant's medical record according to IRB standards. Electronic consent forms will be saved under password protection on the secure lab drive. Copies will be printed and stored in the aforementioned binder, away from all other study data. Data are kept in a locked file cabinet within a locked, private office in an office suite (i.e., behind two locked doors). The participant's study ID number will be recorded on every paper page of the study documents. A centralized database for all outcomes will be saved on the University of Michigan secure server as a password-protected file only accessible by approved study personnel.

The participants' PET amyloid and tau data will not be requested or added to this database until completion of Part I Education & Decision-Making Assessment, to ensure no implicit bias in the manner in which Part I procedures are conducted based on participant risk. At this time, data from eligible participants enrolled in the Part II Disclosure will be accessed. De-identified participant information, coded with the parent study ID number, will be shared with the study team as a secure excel database and transferred to the centralized study database.

3.5.2 Statistical Design

Data Screening

Prior to statistical analyses, data screening will be conducted. Initial steps will include a missing data analysis to determine randomness of missing data and range checks to assess for data quality. Additional screening for univariate and multivariate outliers, skewness and kurtosis will be conducted to inform needs for data transformation and statistical approach.

Statistical Approach

To assess Aim 1, we will compare the proportion of individuals in each diagnostic group who request vs. completed disclosure using a chi-squared test. Similarly, we will test hypotheses associated with Aim 2 (*greater disclosure decisional capacity in MCI than DAT*) by comparing the proportion of individuals in the DAT and MCI groups who demonstrate 'pass' scores on the DDMAT using a chi-squared test. We will also explore which particular elements of decision-making capacity may be more impaired in each group by comparing proportion of each diagnostic group who can adequately demonstrate understanding, appreciation, rationale, and communication on the DMAT using the same statistical strategy. To evaluate Aim 3, (*psychological reactions based on biomarker status*) we will compare participants' and co-participants' responses on outcome measures, based on amyloid and/or tau positivity vs. biomarker negativity. As we expect outcome measures to be correlated, we will utilize a 2 (diagnosis: MCI vs. DAT) by 2 (biomarker status: positive vs. negative) repeated measures analysis of variance (rmANOVA) approach for each follow-up time point. We will also compare differences in psychological reactions between participants and co-participants by diagnosis (MCI vs. DAT) using a paired t-test on all continuous items and a chi-squared test on categorical items. To evaluate Aim 4 (*impact of biomarker disclosure on co-participant caregiving readiness and self-efficacy*), we will similarly compare co-participants' responses, based on amyloid and/or tau positivity vs. biomarker negativity. As we expect outcome measures to be correlated, we will utilize a 2 (participant's diagnosis: MCI vs. DAT) by 2 (biomarker status: positive vs. negative) repeated measures analysis of variance (rmANOVA) approach for each follow-up time point.

SECTION 4: MONITORING

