The current project leverages a robust recruitment and characterization pipeline formed through the Stimulation to Improve Memory study (STIM; R01AG058724) as well as empirically-derived methods from the Sharing Alzheimer’s Risk Estimates (SHARE; R03AG063222-01) study. STIM will ultimately enroll up to 240 individuals with mild cognitive impairment (MCI) and dementia of the Alzheimer’s type (DAT) to evaluate the dose-response relationship associated with transcranial direct current stimulation. Each participant receives both amyloid and tau positron emission tomography (PET), which are used as participant-specific factors that may affect tDCS efficacy. We did not include biomarker disclosure in STIM because it was outside of the scope of the intervention-related focus. Moreover, it was not clear at the time of the initial submission whether participants would be interested in receiving feedback about their biomarker status. Approximately 3 recruiting quarters into the study, there is now substantial evidence that participants **want** the information. Thus, the STIM infrastructure provides an ideal testbed for developing/refining feedback methods for cognitively symptomatic individuals. To improve enrollment and in response to overwhelming interest in biomarker disclosure, we are also opening up this study to participants from other studies co-enrolling through the Michigan Alzheimer’s Disease Research Center that include PET amyloid (and tau, if available) imaging, as long as they meet other criteria detailed above. These additional ‘parent’ studies include the Driving and Physiological Responses (DAPR; HUM00183327), Brain-Behavior Characterization (BBC; HUM00200763) and Dementia in African American Population Phenotyping from Potential Elevated Risk (DAPPER; HUM00152159) studies.

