We have **preliminary data**, acquired from Co-I [name]’s R03-funded study investigating older participants’ interest in biomarker-based feedback, that shows a clear majority of participants have moderate-strong interest in learning their amyloid and tau status (Table 1). In fact, these initial data indicate that participants have equal if not stronger interest in biomarker disclosure as compared to other sources of health information (Table 1). Furthermore, 100% of participants interviewed to date would elect to learn their Alzheimer’s-related biomarker status if it were available, regardless of race, gender, or whether they were cognitively symptomatic or healthy. These findings mirror preliminary data gathered from those currently

[figure not shown]
Table 1. Preliminary Biomarker Disclosure Interest Data

Interest Level	Clinical Information	Structural Neuroimaging	APO-E Genotype	Amyloid/Tau Status
No Interest	0 (0%)	0 (0%)	0 (0%)	0 (0%)
Very Minimal Interest	0 (0%)	0 (0%)	0 (0%)	0 (0%)
Neutral Interest	0 (0%)	1 (6%)	1 (6%)	0 (0%)
Moderate Interest	1 (6%)	1 (6%)	1 (6%)	2 (12%)
Strong Interest	15 (94%)	14 (88%)	14 (88%)	14 (88%)
Would you engage in elective disclosure about your risk for AD based on these variables?				
No	0 (0%)	0 (0%)	0 (0%)	0 (0%)
Yes	16 (100%)	16 (100%)	16 (100%)	16 (100%)

enrolled in STIM (in which the study team does NOT mention disclosure options): of the 31 enrolled participants, 42% spontaneously requested feedback about their amyloid and tau imaging, and 23% mentioned significant disappointment or distress that the current protocol does not allow for disclosure of this information. Additionally, two participants were previously interested in the study but declined to enroll after learning that feedback was not currently provided.

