Preliminary data gathered from the Stimulation to Improve Memory (STIM) study and an associated research project have highlighted several unforeseen but compelling needs in regards to sharing of Alzheimer's disease (AD) biomarker information with research participants and patients alike. The proposed ethics supplement addresses three of these needs, each of which represents an ethical dilemma underlying the communication gap in AD biomarker research: 1) the withholding of biomarker information from interested participants, 2) the unknown ability of cognitively symptomatic patients to appreciate risks and benefits of biomarker disclosure, and 3) the psychological ramifications of biomarker disclosure in cognitively impaired patients. We will leverage STIM infrastructure to systematically address these questions through three specific aims:

Aim 1 investigates interest in, and follow through with, amyloid and tau status disclosure in individuals diagnosed with MCI and DAT. At the time of study enrollment, we will offer all parent study participants the opportunity to learn their amyloid and tau status upon completion of parent study procedures; recording preference as appropriate. We will then examine follow through rates (i.e., interested vs. completed disclosures) thereby extending the literature. We predict *an equally high interest in, and completion of, disclosure regardless of diagnosis.*

Aim 2 examines whether cognitively symptomatic participants demonstrate decision-making capacity as it relates to biomarker disclosure. The question of whether research participants can demonstrate decision-making capacity for biomarker disclosure has, to our knowledge, never been addressed in cognitively symptomatic individuals. Thus, we fill a critical void by evaluating whether such “patients” adequately demonstrate the fundamental elements of decision-making capacity (understanding, appreciation, rationale, communication)¹⁷. Prior to disclosure, we will use a standardized, clinician-rated measure to evaluate capacity. *We predict a main effect of diagnosis where DAT participants demonstrate poorer decisional capacity relative to MCI.* Importantly, we overcome this predicted difference by providing disclosure to either the impaired participant’s legally authorized representative or their healthcare provider. In this way, we ensure the desired information is relayed to each interested participant while still achieving the study aims.

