SECTION 3.1 Participants: Inclusion & Exclusion Criteria

The proposed supplement directly extends STIM study infrastructure (Figure 2). All participants will complete parent study procedures (including amyloid and tau PET) before engaging in the activities of this supplement.

Participants: All participants (i.e., those with MCI and DAT) enrolled in STIM (HUM00146180) will express their interest in biomarker disclosure (Aim 1); however, only those who actually complete PET imaging will be eligible to receive this information (otherwise there is no information to disclose). Specific inclusion and exclusion criteria for STIM are included below:

STIM Inclusion Criteria:

- (1) Diagnosis of MCI or DAT
- (2) Age 55 and older
- (3) MRI-compatible
- (4) Stable on medications for 4 weeks prior to study enrollment

STIM Exclusion Criteria:

- (1) Other neurologic disease (e.g., epilepsy, stroke, traumatic brain injury)
- (2) Psychiatric conditions (e.g., moderate-severe depression, bipolar disorder, schizophrenia)
- (3) Sensory impairments that limit the ability to take part in the study
- (4) A significant history of, or current alcohol or drug abuse/dependence
- (5) Are left-handed with right hemisphere language lateralization

We will additionally invite participants who have completed PET amyloid (and ideally tau) scans through other MADRC-co-enrolled studies (DAPR [HUM00183327], BBC [HUM00200763] and DAPPER [HUM00152159]) to take part in this bioethics supplement, provided they have a diagnosis of MCI or DAT and meet with the additional study-specific criteria below.

Additional inclusion/exclusion criteria for the Education portion of the study are included below:

Part I Education Inclusion Criteria:

- (1) Complete and interpretable PET amyloid and tau imaging
- (2) For those completing virtual sessions: Laptop, desktop, or tablet with 9/7" diagonal diameter and stable, secure internet connection
- (3) Established relationship with a primary care provider, geriatrician, and/or mental health professional
- (4) Co-Participant – required for individuals with DAT; strongly encouraged for participants with MCI

Part I Education Exclusion Criteria:

- (1) Baseline active depression or anxiety or clinically elevated scores on Geriatric Depression Scale – 15 (GDS-15)²⁵⁻²⁶ or Beck Anxiety Inventory (BAI)²⁷⁻²⁸
- (2) History of significant neurological disease
- (3) Current severe or untreated substance use disorder

Part II Disclosure Inclusion Criteria:

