- (1) Demonstrated intact decisional capacity for amyloid and tau PET disclosure

Part II Disclosure Exclusion Criteria: No additional criteria

For the proposed study, we will offer all of the participants who have completed all parent study procedures up to and during this one-year supplement funding period (we estimate up to 100 individuals) the opportunity to enroll in the supplement-related procedures.

Co-Participants: Co-participants are required for all participants with a diagnosis of DAT, given the likelihood that participants may have impaired decision-making capacity and/or need additional support following disclosure. Co-participants are also strongly recommended, though not required, for participants with a diagnosis of MCI except in the event a participant with MCI demonstrates impaired decision-making capacity, thus requiring a co-participant. Co-participants are defined as (a) those who are currently serving as a

caregiver to the participant, or would hypothetically serve in this role should the need arise; (b) individuals who know the participant well, as demonstrated by a relationship lasting at least five years, and contact (any modality) at least once per week. Co-participants must also be age 18 years or older, English-speaking, cognitively healthy, and without current severe or untreated depression and/or anxiety.

Of note, if participants have a dedicated legally authorized representative (LAR) or durable power of attorney (DPOA) for medical and/or research decisions, this individual must serve as the co-participant in order for the participant to take part in the study. Documentation of this legal designation must be provided.

SECTION 3.2 Recruitment Strategy

Participants for Part I: Education will be recruited from parent studies via invitation only. The study team will review participants who completed the parent study, screen these cases for any interim changes that might impact eligibility of the participant (or co-participant, if there is one), and contact dyads to determine interest in engaging in STIM+ Education.

All participants who demonstrate decisional capacity for disclosure (or have a co-participant or LAR/DPOA who demonstrate decisional capacity for disclosure) will be invited to take part in Part II: Disclosure by study team invitation.

SECTION 3.3 Procedures

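### Aim 1 predicts equal rates of interest and completion in MCI and DAT, but the only planned analysis is a chi-squared test of difference, which cannot support equality

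*Combined protocol and SAP*

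**What the plan says.** Section 2.2, Aim 1, predicts "an equally high interest in, and completion of, disclosure regardless of diagnosis". Section 3.5.2 then gives one sentence of analysis: "we will compare the proportion of individuals in each diagnostic group who request vs. completed disclosure using a chi-squared test". No difference, interval, equivalence margin, significance level or threshold for 'high' is stated for Aim 1, and nothing says how a non-significant result will be read.

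The denominators come from several places:

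- **Interest.** Section 2.2 says "we will offer all parent study participants the opportunity to learn their amyloid and tau status", asked at enrollment. The number asked is not given. Section 3.3.1 also places the question at parent-study enrollment, while the Primary Outcomes entry in the opening summary lists interest before and after Education.
- **Follow-through.** Section 2.2: "We will then examine follow through rates (i.e., interested vs. completed disclosures" and so on, which ties completion to those interested but does not fix the denominator.
- **Completion.** Section 3.1 puts the supplement's size at an upper figure ("we estimate up to 100 individuals") and says "only those who actually complete PET imaging will be eligible to receive this information". Section 3.3.1 approaches only people who have already said they are interested.

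**The concern.** The prediction is of no difference, and the test is built to detect one. With about 100 people at most, a non-significant chi-squared result could come from equal rates or from a gap the study was too small to show, and the test cannot tell these apart. It also says nothing about 'high', since two equally low rates would pass it just as well.

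Interest is Primary Outcome 1 in Section 3.4, and Aim 1 carries a directional statement. Section 2.2 describes only Aim 3 as mainly descriptive. A reader of the final report would therefore expect the result to bear on the prediction.

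The denominator matters too. Interest at entry cannot vary among those approached for Education, because they were approached for being interested. A comparison by diagnosis is informative only among everyone asked. Readers could work out an interval from published counts, but only if the counts refer to a stated group.

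**Working it through.** The documents give no expected rate, margin, power or MCI/DAT split for Aim 1, so there is no planned figure to reproduce. All rates and splits below are assumptions. N = 100 is the documents' upper figure.

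**1. One worked result.** Suppose 48/50 MCI and 43/50 DAT participants complete disclosure.

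- Difference: 0.96 − 0.86 = 0.10. Pooled rate: 91/100 = 0.91.
- Chi-squared = d² / [p(1−p)(1/n1 + 1/n2)] = 0.01 / (0.91 × 0.09 × 0.04) = 0.01 / 0.003276 = 3.05, so p = 0.08.
- Wilson 95% limits: MCI 0.865 to 0.989; DAT 0.738 to 0.930.
- Newcombe lower limit: 0.10 − √[(0.960 − 0.865)² + (0.930 − 0.860)²] = 0.10 − 0.118 = −0.018.
- Newcombe upper limit: 0.10 + √[(0.989 − 0.960)² + (0.860 − 0.738)²] = 0.10 + 0.125 = 0.225.

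(Square roots are taken on unrounded limits.) The test is non-significant, yet the data are compatible with a gap of more than 20 points. Only the interval shows this.

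**2. How often a true 10-point gap is non-significant.** For each pair of true rates, sum Binomial(x; n1, p1) × Binomial(y; n2, p2) over all (x, y) where the uncorrected chi-squared statistic is at most 3.84 (two-sided 0.05). N = 100, MCI rate higher.

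| True rates, MCI vs DAT | MCI/DAT 50/50 | 60/40 | 70/30 | 40/60 | 30/70 |
|---|---|---|---|---|---|
| 90% vs 80% | 70% | 67% | 70% | 75% | 80% |
| 95% vs 85% | 61% | 57% | 57% | 67% | 75% |
| 98% vs 88% | 49% | 45% | 38% | 56% | 72% |
| 100% vs 90% | 25% | 22% | 18% | 44% | 74% |

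**3. What an interval would deliver.** Mean half-width of the Newcombe 95% interval at N = 100 with equal true rates, for splits 50/50, 60/40 and 70/30:

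- both 98%: 8.6, 8.8 and 9.7 points
- both 95%: 10.3, 10.6 and 11.4 points
- both 90%: 12.5, 12.8 and 13.7 points

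**4. Chance that this 95% interval lies inside a margin** (N = 100, equal true rates, same three splits):

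- ±10 points: 6-12% if both rates are 95%
- ±15 points: 19-29% at 90%, 50-65% at 95%, 68-92% at 98%

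**The case against.** The strongest reply is that this is a small, non-randomized study, that the preliminary data point to very high interest (16 of 16 in the earlier study would elect disclosure), and that anyone can compute an interval from the counts. Part of this stands. If rates are close to 100% and MCI is at least half the sample, the chi-squared test detects a 10-point gap more often than not. But the 16 of 16 concerns interest rather than completion and is not split by diagnosis. Nor does it change the logic: a test that fails to reject still does not show equality.

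Several stronger readings are tempting, and the documents do not support them:

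- *A 10-point gap would usually be missed.* This is not general. It holds at 90-95% in the higher group but fails at 98-100% unless DAT is the larger group.
- *The test double-counts people, with requested and completed as the two columns of the table.* The wording allows it, but the next sentence of Section 3.5.2 says the Aim 2 analysis is similar and compares MCI with DAT, and Section 2.2 explains the contrast as follow-through. A between-diagnosis comparison is the likelier intention, so this needs only clearer wording.
- *Section 3.4 contradicts Section 3.3.1 on when interest is measured.* Its phrase about interest after STIM activities may describe when disclosure would happen, not when the question is asked. Only the opening summary, with interest before and after Education, clearly differs.
- *The interest comparison will have 240 people.* That is STIM's eventual ceiling. The supplement is funded for one year, and the 31 already enrolled are described as a setting "in which the study team does NOT mention disclosure options". The number asked is unknown, so neither a sample size for interest nor a cap on follow-through can be calculated from it.
- *The sponsor will report a non-significant result as equality.* The plan does not say so. It is silent on how the result will be read.

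**Conclusion.** As written, the Aim 1 analysis cannot support the Aim 1 prediction. That conclusion is one of logic and needs no assumed figure.

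Its practical size does rest on assumptions. With 100 people and MCI at 50-70% of them, a true 10-point gap in completion is non-significant in roughly 18% to 70% of trials, depending on how close the rates are to 100%, and in up to 80% if DAT is the larger group. Fewer than 100 people would generally make this worse. No figure is claimed for interest, because the number asked is not stated.

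The definition of completion is also not settled. Section 2.2 (Aim 2), Section 3.1 (Part II inclusion), Section 3.2 and the capacity rules in Section 3.3.1 do not give one account of when disclosure goes ahead if the participant lacks capacity. Aim 2 predicts poorer capacity in DAT, so this could affect the two groups differently; the documents do not allow the effect to be sized.

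This is a cheap improvement to the analysis wording. It does not show that the study is too small for its purpose.

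**What to change.** Replace the Aim 1 sentence in Section 3.5.2 with:

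> For interest and for completion, we will report the number and proportion in MCI and in DAT, each with a 95% CI (to address 'high'), and the MCI-minus-DAT difference with a score-based 95% CI (Newcombe or Miettinen-Nurminen), each person counted once. Interest will be analysed among those asked, with those never asked counted separately; completion will be analysed among interested participants approached for Education. Interest before and after Education, a listed primary outcome, will be reported by diagnosis in the same way among Education attendees. A non-significant difference will not be taken as evidence of equal rates; equality will be claimed only if a margin was stated before analysis and the CI lies inside it.

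Also align the opening summary, Section 3.3.1 and Section 3.4 on when interest is measured. Reconcile Section 2.2 (Aim 2), Sections 3.1 and 3.2 and the capacity rules in Section 3.3.1 so that 'completed' has one meaning. Which rule applies is for the study team.

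**Cost.** No added participants or visits. The conclusion becomes more modest: about ±9 to ±14 points on the completion difference at N = 100 for rates of 90-98%, so a formal equality claim is realistic only with a fairly wide margin or very high rates. The real burden is data. Interest among everyone asked needs a record from the parent studies, including people who never join the supplement, and it may not exist for those enrolled before the question was added. Where it does not, restrict the analysis to people with a recorded answer and say so.
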